If the participant is randomized to Group A - They will be given a Fitbit Inspire to track the quality of their sleep and asked to download the Fitbit app to their smartphone. They will be provided with the information necessary to set up their account and instructed how to use the app to track their sleep. Please refer to the included script, *Fitbit Setup Guide* attachment, for more details. They will be asked to wear the Fitbit and record what time they went to bed & woke up in a sleep diary (which will be provided) for one week after the baseline visit, one week before the 3rd visit (in-person), and one week before the 4th visit (in-person). The total number of hours slept per night will be collected for the post-baseline period in Qualtrics via a personalized survey link while data will be collected in person for the other two use periods and recorded in Qualtrics. Upon completion of the third assessment, the UA app will be downloaded to his/her smartphone at no cost and with lifetime access. The participant will be instructed to watch the first module of the app and will review its features with the research team member to ensure they do not have any questions (see *UA Setup Guide* attachment for more details).

If the participant is randomized to Group B - They will be given a Fitbit and the process outlined above will be followed. In addition, the UA app will be downloaded to his/her smartphone and the same process will be followed as outlined above.

Both groups are expected to complete the following tasks / assessments at each research visit:

Baseline – In-person

- Group A will complete the first eight items using a personalized survey link (based on participant ID) via Qualtrics

- Group B will complete the first seven items using a personalized survey link via Qualtrics and the seventh, the GAD-7, will be completed as part of the Unwinding Anxiety assessment.
- Both groups will complete the shape matching task on a study laptop.
 1. Demographics. This form will be filled out in Qualtrics (age, gender, socioeconomic status, employment, education, race/ethnicity, relationship status) (approximately 3 minutes)

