 9. Shape Matching Task. The shape matching task assesses cognitive control, or resistance to distraction. Individuals are presented with probe and target shapes and must decide whether they are the same shape. On some trials a distractor shape will be present, which the individual is instructed to ignore. (approximately 25 minutes)

Module 14 (Group B) or 1 Month (Group A) – Online

- Both groups will receive a personalized survey link via Qualtrics.

1. FFMQ non-reactivity (approximately 1 minute)
2. PSWQ (approximately 3 minutes)
3. MAIA (approximately 5 minutes)
4. PROMIS Sleep & Anxiety (approximately 1 minute)
5. WIS (approximately 1 minute)
6. GAD-7 (approximately 2 minutes)

Module 30 (Group B) or 2 Months (Group A)

- Group A will complete the first five items using a personalized survey link via Qualtrics and the sixth, the GAD-7, will be completed as part of the Unwinding Anxiety assessment.
- Group B will complete the first seven items using a personalized survey link via Qualtrics
- Both groups will complete the shape matching task on a study laptop.
 1. FFMQ non-reactivity (approximately 1 minute)
 2. PSWQ (approximately 3 minutes)
 3. MAIA (approximately 5 minutes)
 4. PROMIS Sleep & Anxiety (approximately 1 minute)
 5. WIS (approximately 1 minute)
 6. GAD-7 (approximately 2 minutes)
 7. Net promoter score (approximately 1 minute)
 8. Shape matching task (approximately 25 minutes)

2 Months post-intervention (Group B) or 4 Months (Group A)

- Both groups will complete the first six items using a personalized survey link via Qualtrics and the shape matching task will be completed on a study laptop.
 1. FFMQ non-reactivity (approximately 1 minute)
 2. PSWQ (approximately 3 minutes)
 3. MAIA (approximately 5 minutes)
 4. PROMIS Sleep & Anxiety (approximately 1 minute)

5. WIS (approximately 1 minute)
6. GAD-7 (approximately 2 minutes)
7. Shape matching task (approximately 25 minutes)

4. Participant Population.

Description of participant population:

We will recruit people who experience sleep disturbances related to anxiety in order to address Aims 1 & 2 of this study. We will recruit people who live within a 30-minute drive of Providence, RI because people who live within close proximity to Providence are more likely to return for follow-up visits and complete the study.

Participants will meet the following criteria:

Inclusion:

1. 18 years or older
2. PSWQ > 40 based on established cut-off suggesting GAD

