The Project Coordinator will check in with participants regarding their experience with the app at 7, 14, and 45 days after they receive access. The purpose of these calls is to encourage engagement with the app in addition to providing a time for the participant to address any questions, comments, likes/dislikes with the Project Coordinator. These will be done via the participants preferred contact method (phone call or text message) and the Project Coordinator will establish preferred times at the baseline assessment. In the event that the Project Coordinator cannot reach the participant, an additional outreach attempt will be made within 24 hours. If this is unsuccessful, no additional contact will be made until the next check-in point. If two consecutive check-ins are missed, an additional email will be sent. Responses may be recorded in Qualtrics and coded solely by participant ID to ensure confidentiality.

5. Recruitment Methods

We will recruit residents who live within a 30-minute drive of Providence, RI primarily using social media advertising (e.g. Facebook, Google AdWords), flyers and info cards, and the Brown Mindfulness Center website.

Social Media

Web page advertisement that briefly describes the study and link to a landing site where potential participants can complete the PSWQ and WIS to determine their eligibility and submit their name, phone number, and email address if interested (see *Landing Page* and *Online Screener* attachments for more details). The contact information will be transferred securely using Stronghold by our Brown-approved consultant, [name] (PSA is already in place). Please see *Social Media Ad* attachment for more details.

Flyers

Physical copies of the flyer will be posted on bulletin boards, in waiting rooms, etc. Digital copies will be provided upon request for use on Facebook, websites, and listservs. Please see *Flyer* attachment for more details.

- Brown University campus and surrounding areas
- RISD campus and surrounding areas
- Cafes, grocery stores (e.g. Whole Foods), community boards

Website

Information about the study will be provided on the Brown Mindfulness Center website along with a link to the landing site where potential participants can determine their eligibility. Please see *MC@B Website Ad* attachment for more details.

Brown Mindfulness Center

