Analyses will be conducted in R using an intent-to-treat approach (ITT). Fischer's exact tests for categorical and Kruskal Wallis tests for continuous variables will be used to determine any between-group differences in baseline demographics. To examine between-group differences in behavioral outcome measures at the primary endpoint (2 months), Welch's t-tests will be used along with Mann Whitney U tests for data that violates the assumption of normality. A series of Generalized Estimating Equations (GEE) will be used to estimate the adjusted intervention effect by regressing change in outcomes at each follow-up on time, group, time*group and confounders identified a priori (using correlation analysis. GEE's are used for longitudinal data in order to account for within-subject covariance over time. False Discovery Rate will be used to correct for multiple comparisons.

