Sleep period time (SPT) will be calculated from the paper sleep diaries (PSDs) by subtracting self-reported bedtime from wake time. Fitbit recorded bedtime, wake time, number of sleep minutes, and number of awake minutes will be used to calculate estimated TST and sleep efficiency (SE). To improve reliability, average estimated TST will only be calculated for participants with ≥ 3 days recorded during each wear period. Analysis will utilize the same approach as described for the behavioral measures with the addition of a complete case (CC) approach; participants who did not complete the baseline wear period will be excluded from analysis. For the ITT analysis, we will compare the robustness of our findings using two statistical approaches for handling missing data. First, we will use inverse probability weighting with propensity scores. This is a two-step method: 1) using logistic regression, the probability of missingness is modeled as a function of baseline covariates and baseline values of the outcome and 2) the inverse of the propensity scores (predicted probabilities of dropout from the first step) serve as weights in our regression model of the outcomes. Provided the data is missing at random (MAR) or that the probability of missingness can be fully explained by observable data, this approach produces asymptotically unbiased estimates. To allow for the possibility that the MAR assumption may not hold, we will also use a second approach, pattern mixture models, in which the distribution of the outcome is assumed to follow a mixture of two distributions: one for those who complete follow up and another for those who do not. We will subsequently examine effects under a per-protocol analysis.

Mediation analyses will be conducted using both the Baron and Kenny four-step approach in addition to causal mediation models. In the causal mediation analysis, we will focus on the natural direct and indirect effects and use the bootstrap method with 1,000 bootstrapped resamples to compute the standard errors and 95% confidence interval.

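### As written, the inverse probability weights use the probability of dropout instead of the probability of being observed, so the unbiasedness claimed under MAR does not follow

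*Combined protocol and SAP*

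**What the plan says.** The second paragraph of the Statistical Analysis Plan, which deals with sleep outcomes and missing data, says for the ITT analysis that "we will compare the robustness of our findings using two statistical approaches for handling missing data". The first is inverse probability weighting in two steps. In step 1, by logistic regression, "the probability of missingness is modeled as a function of baseline covariates and baseline values of the outcome". In step 2, "the inverse of the propensity scores (predicted probabilities of dropout from the first step) serve as weights in our regression model of the outcomes". The plan then says that, under MAR, "this approach produces asymptotically unbiased estimates". The second approach is pattern mixture models.

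The regression that the weights would enter appears to be the GEE of the preceding paragraph, described as "regressing change in outcomes at each follow-up on time, group, time*group and confounders identified a priori", with the confounders chosen by correlation analysis. No formula, code or other sentence defines the weights differently.

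**The concern.** Both steps name the same event. Step 1 models missingness, and the parenthesis in step 2 says that the scores to be inverted are the predicted probabilities of dropout. Read as written, an observed outcome gets weight 1/p, where p is that participant's probability of dropping out. The method needs 1/(1 − p). The written rule turns the correction round: completers who resemble the dropouts, and should stand in for them, get the smallest weights.

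The method is there to show whether the ITT result survives missing data. With inverted weights, a gap between weighted and unweighted results could come from the weights alone, and agreement would give no reassurance.

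A smaller, separate point is that the missingness model does not name randomized group, although the design makes dropout likely to work differently by arm. Under Procedures, the third assessment is tied to Module 30 in Group B but to 2 months in Group A. Under Check-ins, staff will "check in with participants regarding their experience with the app at 7, 14, and 45 days after they receive access". For Group A, access comes late: "Upon completion of the third assessment, the UA app will be downloaded to his/her smartphone". Before the primary endpoint, therefore, only Group B gets these calls.

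**Working it through.** The plan gives no figure for the weights, so there is none to reproduce. Its only related numbers, under Participant enrollment target, are 64 complete data sets from 80 enrolled: 1 − 64/80 = 20% loss. Every other input below is an assumption.

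**1. Algebra.** A participant with baseline X is observed with probability 1 − p(X).
- Weight 1/(1 − p): expected weight (1 − p) × 1/(1 − p) = 1 at every X. The randomized sample is restored.
- Weight 1/p: expected weight (1 − p)/p, the odds of being observed. This is constant only if p is constant, when no weighting is needed.

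| p | weight as written, 1/p | correct weight, 1/(1 − p) |
|---|---|---|
| 0.10 | 10 | 1.11 |
| 0.40 | 2.5 | 1.67 |

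**2. Example by hand.** Take two equal baseline strata with dropout 10% and 30% in both arms, and effects 0.25 and 0.75 (true mean 0.50). The estimate is 0.25 + 0.50 × (share of the second stratum).
- Unweighted: share = 0.35/(0.45 + 0.35) = 0.4375; estimate 0.469.
- Correct: share = 0.5; estimate 0.500.
- As written: 0.5 × 0.9/0.1 = 4.5 and 0.5 × 0.7/0.3 = 1.167; share = 1.167/5.667 = 0.206; estimate 0.353.

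The bias is −0.147 as written, against −0.031 with no weighting.

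**3. Simulation with the plan's dropout model (baseline only, no group).** Baseline x ~ N(0,1). Outcome y = 0.6x − 0.5g + h·g·x + error (SD 0.8), with g = 1 for Group B and 1:1 arms. Logit P(dropout) = −1.5 + s·x in both arms. Change is y − x. Estimates come from samples of two million or more.

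| s | h | as written (true −0.50) |
|---|---|---|
| 0.8 | 0.2 | −0.66 |
| 0.4 | 0.2 | −0.58 |
| 1.2 | 0.2 | −0.74 |
| 0.8 | 0.1 | −0.58 |
| 0.8 | −0.2 | −0.34 |
| 0.8 | 0 | −0.50 |

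In the first row (about 21% dropout), no weighting gives −0.53 and the correct weights give −0.50. Adding baseline as a main effect leaves the written rule at −0.66.

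**4. Precision.** With s = 0.8, h = 0 and 4,000 trials of 80 participants, the SE of the change-score difference is 0.22 unweighted, 0.33 as written and 0.24 correct. The effective size of the completers, (Σw)²/Σw² over their number, is 61% as written and 97% correct: of 64, about 39 against 62. For the written rule it is about 90% at s = 0.4 and 30% at s = 1.2.

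**5. Group term.** Let dropout depend on baseline in Group B only (s = 0.8 in B, 0 in A; h = 0; 19.6% dropout). The true effect is −0.50.

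| weights | raw outcome | change |
|---|---|---|
| none | −0.59 | −0.44 |
| as written, no group in dropout model | about −0.58 | about −0.45 |
| 1/(1 − p), no group in dropout model | −0.60 | −0.43 |
| 1/(1 − p), fitted by arm | −0.50 | −0.50 |

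Here a dropout model without group cannot remove the bias, whichever way it is inverted.

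**The case against.** The strongest reply is that this is a wording slip. The plan names a standard method and its standard property, and only the parenthesis departs from them; an analyst who knows the method would code it correctly. That may be so, and the criticism is of the rule as written. But both steps name the same event and nothing else defines the weights.

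The harm is also conditional, and this stands. Bias is zero if dropout acts alike in both arms and the effect does not vary with baseline, or if the outcome model correctly includes the predictors of dropout. The confounders chosen by correlation analysis might include baseline, but the plan does not say so, and a baseline main effect does not protect when the effect varies with baseline. The base-case bias of 0.16 is about half the SE of 0.33 at 80 participants. With baseline in the model the loss of precision is smaller: SEs of about 0.20 unweighted, 0.26 to 0.27 as written and 0.21 correct.

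The inverted weights are not always the worse choice. When dropout depends on baseline in Group B only, they come marginally closer to the truth than no weighting or the corrected weights without group. That shows the missing group term, and does not support the inversion: inverted weights fitted by arm move the raw estimate to about −0.98.

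The group term itself is a trade-off. Assignment precedes the baseline assessments, so an unlisted covariate set does not exclude it, and different dropout by arm is inferred from the design.

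Reach is limited. The Welch and Mann-Whitney tests, the complete-case analysis and the pattern mixture models do not use these weights. Because the text sits in the sleep paragraph, it is unclear whether weighting also applies to the behavioral outcomes.

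**Conclusion.** The concern holds. The only weight the plan defines is 1/P(dropout), and the unbiasedness it claims under MAR is not a property of that weight in general. This follows from the algebra and needs no assumed inputs.

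The size does rest on assumptions. With 19% to 23.5% dropout related to baseline alike in both arms, and an effect that varies with baseline, the written rule misses a true −0.50 by 0.08 to 0.24 in either direction; in the base case no weighting misses by 0.03. Without that variation there is no bias, but the SE is about half as large again as with no weighting (0.33 against 0.22). It should be fixed before analysis. It affects a supporting analysis and leaves the primary comparison untouched.

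**What to change.** Rewrite step 2 as a whole, since changing only the parenthesis would still leave the missingness scores being inverted. For example: *participants with an observed outcome are weighted by 1/(1 − predicted probability of dropout) in the outcome regression*. This is one sentence and has no downside.

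Separately, state that the missingness model is fitted by arm, or includes group and its interaction with the baseline outcome. This costs parameters: about 16 expected dropouts (80 − 64) support few terms, so the covariate list should be short and named in advance. The inversion must be corrected first, because adding group to inverted weights can make the bias worse. The same edit could say which outcomes the weighting covers.

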 2. Five Facet Mindfulness Questionnaire (FFMQ) non-reactivity scale. The non-reactivity scale is a subscale of the 39-item FFMQ which is a self-report psychological measure of mindfulness skills. This subscale contains 7 items which are presented on a 6-point Likert scale ranging from 1 (almost always) to 6 (almost never). This questionnaire is included in the protocol. (approximately 1 minute)
 3. Penn State Worry Questionnaire (PSWQ). The PSWQ is a 16-item self-report measure of worry with items presented on a 5-point Likert scale ranging from 1 (not at all typical of me) to 5 (very typical of me). This questionnaire is included in the protocol. (approximately 3 minutes)
 4. Multidimensional Assessment of Interoceptive Awareness (MAIA). The MAIA is a 32-item self-report questionnaire comprised of 8 subscales including: noticing, not-distracting, not-worrying, attention regulation, emotional awareness, self-regulation, body listening, and trusting. Items are rated on a 6-point Likert scale ranging from 0 (never) to 5 (always). This questionnaire is included in the protocol. (approximately 5 minutes)
 5. PROMIS Sleep & Anxiety items. The PROMIS Sleep & Anxiety includes 5 questions taken from the PROMIS v1.0 Sleep Disturbance questionnaire which focus on the interaction between worry and sleep. This questionnaire is included in the protocol. (approximately 1 minute)
 6. Worry Interfering with Sleep scale (WIS). The WIS is a single item self-report question that asks individuals to rate what percent of time worry interfered with their ability to get to or stay asleep. This questionnaire is included in the protocol. (approximately 1 minute).
 7. Expectancy. These three questions assess treatment usefulness, confidence, and likelihood to recommend on a 9-point Likert scale from 1 (Not at all confident or Not at all useful) to 9 (Very confident or Very useful) and from 0 to 100%. This questionnaire is included in the protocol (approximately 1 minute).
 8. Generalized Anxiety Disorder 7-items (GAD-7). The GAD-7 is a 7-item measure of anxiety rated on a 4-point Likert scale ranging from 0 (Not at all sure) to 3 (Nearly every day). This questionnaire is included in the protocol. (approximately 2 minutes)

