3. $\geq 5/10$ on Worry Interfering with Sleep scale (WIS)
4. Able to read and speak English, because the Unwinding Anxiety app is available in English only.
5. Owns a smartphone (UA app can only be used on a smartphone)
6. Willingness to wear the Fitbit Inspire tracker

Exclusion:

1. If using psychotropic medication - not on a stable dosage for at least 6 weeks
2. Medical disorder of the severity that would interfere with ability to participate (e.g. cancer, multiple sclerosis, Parkinson's disease, ALS, etc. These disorders impact sleep quality which could confound study outcomes.)
3. As needed (i.e. prn) benzodiazepine or hypnotic sleep aid
4. Known sleep disorder (e.g. obstructive sleep apnea, restless leg syndrome – because these disorders impact sleep quality.)
5. Psychotic disorder (Mindfulness meditation has to be carefully monitored with people experiencing psychosis. We are not able to provide this type of monitoring given budget constraints.)
6. Post-Traumatic Stress Disorder (Mindfulness meditation has to be carefully monitored with people experiencing PTSD. We are not able to provide this type of monitoring given budget constraints.)
7. Severe Depression (PHQ-2 score > 3) (People experiencing severe depression may also experience sleep disorders which could confound study outcomes.)
8. Current shift work employment (People working alternate shifts may have sleep quality problems which could confound study outcomes.)
9. BMI > 30. (People who are obese may have sleep quality problems which could confound study outcomes.)
10. Evening caffeine use (Caffeine use late in the day can impact the quality of a person's sleep, hence the possibility of confounding study outcomes.)
11. Pregnancy (Women in various stages of pregnancy often have sleep quality problems, hence the possibility of confounding study outcomes.)
12. New parents whose child is not sleeping through the night (New parents are often awakened every 3 – 4 hours by a newborn which could confound study outcomes)
13. Lives in same household as someone already enrolled in this study (To prevent study participants from sharing study information with one another.)

Participant enrollment target:

Our goal is to collect 64 complete and usable data sets, so our plan is recruit and enroll 80 participants.

Enrolling 80 participants will be sufficient to cover any participants who don't complete the study and it will allow us to meet our N of 64.

Check-ins

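### With 1,000 bootstrap resamples, a borderline mediation interval can change its verdict with the random seed; 10,000 resamples would reduce this at almost no cost

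*Combined protocol and SAP*

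**What the plan says.** The mediation text is the last paragraph of the Statistical Analysis Plan. It names two methods: "Mediation analyses will be conducted using both the Baron and Kenny four-step approach in addition to causal mediation models". For the causal models, "we will focus on the natural direct and indirect effects", and the plan is to "use the bootstrap method with 1,000 bootstrapped resamples to compute the standard errors and 95% confidence interval". It does not state a seed, the type of bootstrap interval (percentile, bias-corrected or normal from the bootstrap standard error), the mediators, the outcomes or the number of models. It gives no reason for the figure of 1,000 and no precision target.

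Multiplicity is handled in one sentence: "False Discovery Rate will be used to correct for multiple comparisons". That sentence closes the plan's opening paragraph, on baseline comparisons, the 2-month between-group tests and the GEE models. Mediation has not yet been introduced at that point. The level q, the family and the number of tests are not given.

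The sample size is in section 4, under the enrollment target: "Our goal is to collect 64 complete and usable data sets, so our plan is recruit and enroll 80 participants".

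**The concern.** A bootstrap interval has two sources of error: sampling of participants, and the finite number of resamples. Only the second can be reduced at the analyst's desk. A 95% percentile limit uses the outer 2.5% of the draws, so with 1,000 resamples few draws determine it. If mediation is judged by whether the interval excludes zero (a natural use, though the plan does not state it), a result near the boundary could pass with one seed and fail with another. With no seed specified, the plan also leaves room to re-run a borderline interval. What is at stake is the reproducibility of borderline claims about mechanism, not the trial's main comparison.

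**Working it through.** The documents give no inputs from which 1,000 could be derived, so there is no figure to reproduce. The check is how much Monte Carlo error that number leaves.

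**Inputs.** From the Statistical Analysis Plan: B = 1,000 resamples and a 95% interval. From section 4: 64 complete data sets, 80 enrolled. Assumed: equal tails (2.5% each), a roughly normal bootstrap distribution and, for the simulations, the path sizes.

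**Step 1. Error of a limit at B = 1,000.**
- Draws per tail: 1,000 × 0.025 = 25.
- Standard error of the tail proportion: √(0.025 × 0.975 / 1,000) = 0.0049. A two-sided bootstrap p-value near 0.05 thus has a standard error of about 0.010.
- Percentile limit: √(p(1−p)/B) / φ(z_p), in units of the estimate's standard error, is about 0.084, or about 2.2% of the interval's width.
- Normal-type limit: the bootstrap standard error has relative error 1/√(2B) = 1/√2,000 = 2.2%, so the limit moves by 1.96 × 0.0224 = 0.044 standard errors.

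**Step 2. When two seeds disagree.** Let q be the chance that one run's percentile interval excludes zero, from a binomial count with B draws and probability p/2, where p is the two-sided p-value at infinite B. Two runs disagree with probability 2q(1−q):

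| Underlying p | B = 1,000 | B = 10,000 |
|---|---|---|
| 0.02 | 0.00 | 0.00 |
| 0.03 | 0.02 | 0.00 |
| 0.035 | 0.08 | 0.00 |
| 0.04 | 0.23 | 0.001 |
| 0.045 | 0.41 | 0.09 |
| 0.05 | 0.50 | 0.50 |
| 0.055 | 0.44 | 0.12 |
| 0.06 | 0.29 | 0.003 |
| 0.07 | 0.07 | 0.00 |
| 0.08 | 0.01 | 0.00 |

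At 1,000 resamples the sensitive zone is about 0.03 to 0.08. At 10,000 it shrinks to about 0.045 to 0.055. No finite B removes the disagreement exactly at the boundary.

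**Step 3. How often a trial lands in that zone.** The simulations used linear models and percentile limits, with two independent bootstraps per data set.

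| Completers | Assumed paths (SD) | Data sets | Power | Disagree, B = 1,000 | Disagree, B = 10,000 |
|---|---|---|---|---|---|
| 64 | 0.5 / 0.3 | 500 | 31% | 3.2% | 1.6% |
| 64 | 0.6 / 0.35 | 500 | 52% | 4.4% | 1.2% |
| 64 | 0.5 / 0.3 | 1,000 | 29% | 3.3% | not run |
| 64 | 0.8 / 0.4 | 1,000 | 75% | 3.3% | not run |
| 80 | 0.5 / 0.3 | 1,000 | 42% | 5.2% | not run |
| 80 | 0.8 / 0.4 | 1,000 | 87% | 2.6% | not run |

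A further check with 64 completers gave about 5% at 1,000 resamples and about 2% at 10,000. These rates carry simulation error of their own. With 500 data sets, 3.2% has standard error √(0.032 × 0.968 / 500) = 0.8 percentage points, and 1.6% has √(0.016 × 0.984 / 500) = 0.6. The rates are therefore best read as roughly 3-5% against 1-2%.

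**Step 4. Comparison with sampling error.** Two independent repeats of the whole trial would disagree with probability 2 × power × (1 − power). That is 2 × 0.31 × 0.69 = 43% and 2 × 0.52 × 0.48 = 50% in the first two scenarios, more than ten times the seed effect.

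**Step 5. If FDR were applied to bootstrap tail p-values (not in the plan).** At an assumed q of 0.05 with m tests, the strictest Benjamini-Hochberg step uses a two-sided level of 0.05/m. The draws per tail are then 1,000 × 0.05/(2m) = 25/m: 12.5 for m = 2, 5 for m = 5, 3.1 for m = 8 and 1.25 for m = 20. Later steps are looser, up to 25. With 10,000 resamples every count is ten times larger.

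**The case against.** The strongest reply is that 1,000 resamples is adequate for what the plan specifies. In the simulations two seeds agree in about 95% of trials or more. The bootstrap standard error is accurate to about 2%. A normal-type interval, which the wording allows, halves the error of the limit. The Baron and Kenny analysis runs alongside and needs no seed. Mediation is separate from the 2-month endpoint, and no stated precision target is missed. All of this stands, and it keeps the point minor. It does not remove the point, because the error is avoidable and the Baron and Kenny steps do not supply the interval for the natural indirect effect.

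A reader might also draw stronger conclusions that the documents do not support:

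- *That only about 3 draws lie in each tail.* The plan specifies a 95% interval, so the count is 25. Reaching 3 requires FDR to cover mediation, bootstrap tail p-values, about 8 tests, q = 0.05 and the strictest step. None of these is stated. The MAIA has 8 subscales, but nothing links them to a mediation family.
- *That mediation conclusions depend on the seed rather than on the data, or that many limits will lie near zero.* Steps 2 to 4 show an effect confined to borderline results and small beside sampling error.

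**Conclusion.** The concern holds in a limited form. With 1,000 resamples and percentile limits, Monte Carlo error in each limit is about 0.084 of the estimate's standard error. A different seed can then change whether the interval excludes zero when the underlying p-value is about 0.03 to 0.08. The overall rate is roughly 3-5% of trials per indirect effect, falling to about 1-2% with 10,000 resamples. These rates rest on assumed moderate paths, linear models, percentile limits and 64 completers. They would be lower for normal-type limits. The FDR calculation is conditional on a choice that the plan does not make, and should be read as the range 25/m. The 2-month between-group comparison is unaffected. This is an optional improvement in precision and reproducibility, not a flaw that threatens the trial's conclusions.

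**What to change.** In the last paragraph of the Statistical Analysis Plan, replace the 1,000 with *at least 10,000 bootstrapped resamples with a pre-specified, reported seed*. Draws per tail rise from 25 to 250, and the error of a percentile limit falls from 0.084 to 0.027 standard errors. The two parts do different work: the larger number reduces Monte Carlo error, while the seed only makes the result reproducible and rules out selective re-runs.

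The cost is a few minutes of computing, with no effect on participants, sample size or data collection. Nothing in this check shows that a particular interval type or resampling within arm is needed. If the sponsor does intend FDR to cover mediation, the plan should say so and define the family, because the required number of resamples then depends on m.
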